**IV. Protocol**

Among Veteran smokers with chronic moderate to severe pain, a pain intensity  $\geq 4$  for 3 or more months, we are proposing a randomized comparative effectiveness trial to compare the effectiveness of a telephone-based smoking cessation intervention including CBI for pain to a standard telephone-based smoking cessation intervention. The goals of the study are: 1) Evaluate the impact of **smoking cessation plus CBI (SMK-CBI)** on cigarette abstinence rates among Veterans with chronic pain at 6 and 12-months compared to **standard smoking cessation counseling (SMK-STD)**; 2) Evaluate the impact of **SMK-CBI** on pain intensity and pain interference among Veterans at 6- and 12-months compared to **SMK-STD**; 3) Assess whether change in self-efficacy and pain-related anxiety mediate the impact of **SMK-CBI** on smoking cessation in Veterans with pain at 6- and 12-months compared to **SMK-STD**.

**6. Research Plan:**

**Study methods with proactive recruitment:** Potentially eligible patients will be identified by administrative data pull of pain scores equal to or greater than 4 and current tobacco use. We will oversample women Veterans to increase the diversity. Eligible patients will be sent the following components: Introductory letter: A letter from [name] to introduce the study, make an appeal to the patient to quit smoking, and informs them that they will be called to complete a telephone survey unless they call a toll-free number to refuse participation; Informational Consent Document: A document providing all the information for informed consent into the study and will be sent along with introductory letter and that describes the study.

**Other recruitment methods:** Recruitment will also occur via flyers posted in patient care areas, referrals by providers, and self-referrals from Clinicaltrials.gov at VACHS and VA Central Western Massachusetts Healthcare System (VACWM), and with the monthly pain recruitment table at West Haven and Newington. The anticipated goal for this VACHS study is to recruit 371 veterans, and VACWM will look to recruit 100 Veterans.

Approximately seven days after the mailing, Veterans who have not opted out will receive a phone call from a research assistant (RA) to further assess inclusion criteria, obtain informed consent (if interested), and conduct the baseline survey. Eligible patients must be Veterans enrolled at VACHS or VACWM with current tobacco use, willingness to make a quit attempt in the next 30 days, significant pain defined as  $\geq 4$  on the pain intensity portion of the BPI, and report that their current pain has been present for 3 months or more. Veterans with any of the following will be excluded: active diagnosis of psychosis or dementia in their medical records, Non-english speaking, refusal to provide informed consent, severely impaired hearing or speech, lack of telephone access, enrollment in another research study that might affect the main outcomes of this study, or terminal illness. Participants enrolled into PASS will have a research alert noted in their medical record.

In this comparative effectiveness trial, both groups will receive 5 sessions of telephone counseling. Five counseling sessions will be completed over 10-12 weeks on an approximately bi-weekly schedule that will be tailored to the individual Veteran's needs. Veterans will be mailed a reminder letter about their 6 month and 12

month follow-up surveys in order to improve retention. Both VA sites will utilize the same counselor for the telephone sessions.

**Data sharing plan:** Electronic data will be stored on a VA protected SharePoint site or local network, both of which are secure systems that exists behind the VA firewall and access is granted by an administrator only to authorized users. A SharePoint website is established only for the purposes of this project and will serve as a repository for study documents, communication, and other important information to be shared between VA CT and VACWM. The site is private and can only be accessed by approved study personnel with permissions granted by the PI or Project Director.

**Smoking cessation counseling:** Both groups will receive smoking telephone counseling and smoking cessation content delivered at parallel times. The protocol included in this application is based on standard techniques shown to be efficacious for smoking cessation and is informed by behavioral treatment principles, Social Cognitive Theory, and Motivational Interviewing. The treatment protocol is consistent with the Public Health Service Clinical Practice Guide and was tailored to the Veteran population based on principles of evidence and consensus-based clinical practices.

**Cognitive behavioral intervention:** In the SMK-CBI arm, behavioral stress reduction pain management approaches will be integrated into the evidence-based smoking cessation counseling. The adjunctive cognitive behavioral intervention emphasizes psycho-educational and skills-based approaches and is informed by VHAs existing pain self-management program. Specifically, the CBI developed for the study includes a focus on increasing physical activity, identifying pleasurable activities, relaxation practices, and thought monitoring/restructuring. The CBI participant manual will also include PASS activity booklet. The main objective of the PASS activity booklet will be to provide Veterans with an opportunity to practice selected behavioral and cognitive skills of relevance for both smoking cessation and pain self-management. Participants in the SMK-CBI arm will be given pedometers. This group will be instructed to track and record their weekly steps in the PASS activity booklet, and will be asked to report their weekly steps to the PASS counselor during each of the 5 telephone counseling sessions.

**Counselor education:** The PASS study counselor will be trained by a doctoral-level clinician on both SMK-STD and SMK-CBI counseling sessions, will be provided with videos and readings on CBI, smoking-cessation, and pain, and will be audio-recorded using a mock patient. The PASS study counselor will be given the opportunity to ask questions about trainings, and will then be tested and rated by a doctoral-level clinician using the Fidelity Scale to establish proficiency.

**Standard of Care:**

At VA specialty-based smoking clinics, counseling sessions with NRT are standard care for assisting Veterans to quit smoking. At the first telephone counseling session, counselors will ask potential participants if they are interested in using NRT. [name] will contact the patient's PCP to facilitate a NRT prescription if the PCP agrees for those participants who are interested in using NRT.

**Table 1: Outline of Counseling Sessions**

| Smoking Cessation Counseling SMK-STD |  | Smoking Cessation Counseling plus Cognitive Behavioral Intervention SMK-CBI   |
|---|--|--|
| #1  | 

✓ Introduce counselor and study

✓ Check in

✓ Explore motivation to quit

✓ Set quit date if appropriate

 | 

✓ All components of SMK-STD Session 1 (to the left, less the quit date discussion), plus the following:

✓ Introduce physical activity

✓ Use pedometer to record weekly step count

✓ Assign homework

 |

|    |   |  |
|----|---|--|
| #2 | 
 
✓ Check in
 
✓ Check in on patient's action plan on taking steps towards quitting
 
✓ Discuss ways to manage cravings
 
       | 
 
✓ All components of SMK-STD Session 2 (to the left), plus the following:
 
 
 
✓ Pleasant activities
 
✓ Set quit date
 
✓ Record weekly step count
 
✓ Assign homework
 
                     |
| #3 | 
 
✓ Check in
 
✓ Check in on patient's action plan on taking steps towards quitting
 
✓ Discuss how to handle slips
 
           | 
 
✓ All components of SMK-STD Session 3 (to the left), plus the following:
 
 
 
✓ Introduce and practice progressive muscle relaxation
 
✓ Record weekly step count
 
✓ Assign homework
 
             |
| #4 | 
 
✓ Check in
 
✓ Check in on patient's action plan on taking steps towards quitting
 
✓ Discuss rewards
 
                       | 
 
✓ All components of SMK-STD Session 4 (to the left), plus the following:
 
 
 
✓ Introduce Unhelpful Thoughts
 
✓ Introduce Mini Practices
 
✓ Record weekly step count
 
✓ Assign homework
 
 |
| #5 | 
 
✓ Check in
 
✓ Check in on patient's action plan on taking steps towards quitting
 
✓ Develop a post-counseling action plan
 
 | 
 
✓ All components of SMK-STD Session 5 (to the left), plus the following:
 
 
 
✓ Review skills learned in previous sessions
 
✓ Record weekly step count
 
  |

## V. Outcomes:

Participants will be surveyed three times: enrollment, 6-months post-intervention and 12-months post-intervention using VA RED Cap to collect these data. Baseline survey will assess demographics, smoking history, nicotine dependence, global self-efficacy to quit smoking, depression, pain intensity and other covariates related to pain and smoking, via telephone. Follow-up surveys will be administered at 6-months and 12 months post-intervention. The follow-up surveys will assess smoking status, pain intensity, use of intervention materials (e.g., NRT, PASS activity booklet), and intervention acceptability (e.g., intervention appropriateness, suitability, effectiveness, and convenience). Participants will be compensated \$25 per completed follow-up survey. We will abide by the patient's preference since many patients may be reluctant to send their sensitive bank information or provide it over the phone for this telephone-based study.

Saliva samples will be collected from participants who report not smoking in the last 7 days (7-day point prevalence) in order to biochemically validate their self-reported smoking status. This process has been shown to improve the validity of self-reported smoking cessation. Samples will be collected at next clinic visit following the telephone interview. Saliva samples will measure cotinine levels using NicAlert dipsticks with a standard cut point of 16 ng/ml to determine abstinence. Participants will receive \$10 incentive for providing each saliva sample.

Counseling session fidelity will be assessed using audio-taped recordings of sessions. We aim to record approximately 20% of sessions (all sessions in the first 3 months of the study and then one week every 2 months for the remainder of the study). Investigators will rate 10% of the sessions to ensure protocol fidelity and lack of drift of information from the SMK-CBI to SMK-STD over time.

**Outcome 1: Prolonged abstinence:** In keeping with the SNRT recommendations for measuring abstinence, we will use prolonged abstinence as our main outcome and allow for a grace period around quit date. During the 6- and 12-month follow-ups, patients will be asked about prolonged abstinence, "In the past 6 months, have

you smoked at least a part of a cigarette on each of 7 consecutive days?" and "In the past 6 months, have you smoked any cigarettes in each of 2 consecutive weeks?"

**Outcome 2: Point prevalent abstinence:** At each follow-up (6-and 12-month), patients will be asked whether they have smoked a cigarette, even a puff, in the past 7 days and, if no, will be asked whether they have smoked a cigarette, even a puff, in the past 30 days.

**Outcome 3: Pain intensity (usual) and pain related functional interference:** Participants will complete the BPI, which includes 2 multi-item scales measuring pain intensity and pain-related functional interference. Pain intensity in the past 24 hours is measured in 4 items—worst, least, current and usual—each using a validated 11-point *numerical rating scale* (0-10). A rating of 0 indicates no pain while 10 indicates the worst pain imaginable. A score of 4 or above is considered a clinically significant pain level according to VHA treatment guidelines. The functional interference subscale consists of 7 items measuring self-rated pain interference related to general activity, mood, walking ability, normal work (inside or outside the home), relations with other people, sleep and enjoyment of life. Respondents rate how much pain has interfered with these aspects of their lives in the past 24 hours on a 0 (does not interfere) to 10 (completely interferes) point scale.

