**E.12.4. Missing Data.** Because the main predictors of interest are collected at baseline, we do not anticipate much missing data in these variables. We do, however, anticipate missing values in the longitudinal outcomes owing to dropout, death, an inability to reach the patient by phone, or item non-response. If the missing values are related to other measured patient factors, such as age, gender, or employment status, then multiple imputation (MI) provides a framework for incorporating information from these auxiliary variables while still preserving a parsimonious main treatment effect model: this framework is described as a significant advantage in recommendations from the Panel on Handling Missing Data in Clinical Trials. We will follow multiple imputation methods presented in Hedeker et al for missing abstinence outcomes. Depending on the type and scope of missing data for other longitudinal variables, MI will be conducted via the SAS procedure PROC MI or the SAS macro IVEware (<http://www.isr.umich.edu/src/smp/ive/>).

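### The saliva check on 7-day abstinence has no time limit after the interview, reads other nicotine as smoking, and leaves self-reported abstainers without a usable sample unscored

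*Combined protocol and SAP*

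**What the plan says.** Section V (Outcomes) describes the check. On who is sampled: "Saliva samples will be collected from participants who report not smoking in the last 7 days". The stated purpose is to "biochemically validate their self-reported smoking status". On timing: "Samples will be collected at next clinic visit following the telephone interview". On reading the result: "Saliva samples will measure cotinine levels using NicAlert dipsticks with a standard cut point of 16 ng/ml to determine abstinence". The same section describes the study as telephone-based ("for this telephone-based study"), and no study visit is scheduled anywhere.

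Outcome 2 in Section V defines 7-day point prevalence by the participant's answer about cigarettes. In Section VI, the text under Hypotheses 1.1 and 1.2 makes abstinence a yes/no variable and says that self-report will be validated by cotinine.

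The Standard of Care paragraph makes NRT available to interested participants if their primary care physician agrees. The follow-up survey asks about "use of intervention materials (e.g., NRT, PASS activity booklet".

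Section E.12.4 (Missing Data) attributes missing outcomes to dropout, death, failure to reach the patient by phone, and item non-response. It applies multiple imputation "for missing abstinence outcomes", with predictors to be used if missingness is "related to other measured patient factors, such as age, gender, or employment status".

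**The concern.** There are three linked gaps.

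**Timing.** The report covers the 7 days before the call, while the sample is taken whenever the participant next attends a clinic. Error can run either way. A relapse after the interview looks like a false report, and a participant who misreported can stop smoking before the visit and pass.

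**Other nicotine.** The outcome is cigarette abstinence, but cotinine reflects nicotine from any source. Under the cut point as written, an abstainer using NRT or another nicotine product is read as smoking. NRT use is surveyed, but nothing links that answer to the cotinine result, and nothing records nicotine use on the day of sampling.

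**No usable sample.** Only self-reported abstainers are asked for saliva, so every late or absent sample belongs to one. That participant answered the survey, so none of the listed causes of missingness clearly applies. Keeping the self-report, counting the person as smoking, and imputing are all open readings. They give different abstinence rates and different power, and without a stated rule the choice would be made after the data are seen.

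**Working it through.** The documents give no abstinence rates, power, alpha, allocation ratio or dropout rate, so there is no figure of the plan's own to reproduce.

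**Inputs**
- From the documents: recruitment goals of 371 + 100 = 471 (section 6, Research Plan). The 95% CI in Section VI is taken as a two-sided 5% test.
- Assumed: 1:1 allocation (235 SMK-CBI, 236 SMK-STD), full survey response, self-reported 7-day abstinence of 22% vs 12% at 6 months, and self-report true. Self-reported abstainers: 235 × 0.22 + 236 × 0.12 = 51.7 + 28.3 = 80.

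**Formulas.** Let p be the self-reported rate and u the share of abstainers recoded.
- Rate when recoded as smoking: p(1 − u).
- OR = [p1/(1 − p1)] / [p2/(1 − p2)].
- Power = Φ(|p1 − p2|/SE − 1.96), with SE = √[p1(1 − p1)/235 + p2(1 − p2)/236].

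**Worked case, u = 20% (16 people).** The rates are 0.22 × 0.8 = 17.6% and 0.12 × 0.8 = 9.6%. SE = 0.0314, and 0.080/0.0314 = 2.55. Power = Φ(0.59) = 72%.

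| Share of abstainers counted as smoking (SMK-CBI / SMK-STD) | Rates | OR | Power |
|---|---|---|---|
| None (self-report kept) | 22.0% vs 12.0% | 2.07 | 83% |
| 5% / 5% | 20.9% vs 11.4% | 2.05 | 81% |
| 10% / 10% | 19.8% vs 10.8% | 2.04 | 78% |
| 20% / 20% | 17.6% vs 9.6% | 2.01 | 72% |
| 10% / 5% | 19.8% vs 11.4% | 1.92 | – |
| 5% / 10% | 20.9% vs 10.8% | 2.18 | – |

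**Other nicotine.** Counseling lasts 10–12 weeks and follow-up is 6 and 12 months after it. Sampling therefore falls roughly 8 and 14 months or more after NRT is raised at the first session. A 2% loss gives OR 2.06 and power 82%; a 5% loss is in the table.

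**Error the other way.** Suppose 3% of smokers misreport and one in five of them passes because of the delay. The rates become 0.22 + 0.78 × 0.006 = 22.5% and 0.12 + 0.88 × 0.006 = 12.5%. That is about 2 people, with OR 2.02 and power 82%.

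**Imputation.** Suppose unsampled abstainers were imputed from arm alone, ignoring the telephone report. The rate is then p(1 − u)/(1 − pu). At u = 20% this is 0.176/0.956 = 18.4% vs 0.096/0.976 = 9.8%, close to counting them as smoking. Imputing by arm among self-reported abstainers only would return 22% vs 12% under these assumptions.

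**Lower rates.** At 15% vs 8%, power is 67% (OR 2.03). It falls to 56% (OR 1.99) when 20% are counted as smoking.

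**The case against.** The strongest reply has four parts.

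1. **Ordinary discordant samples are already scored.** A cut point used to determine abstinence implies that a result at or above it counts against abstinence. This stands. A reader might infer that the plan has no rule for any discordant result, but the text does not support that. The gap lies with late samples, absent samples and users of other nicotine.

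2. **Imputation may already cover unsampled abstainers.** A reader might infer that imputation will ignore the telephone report because the named predictors omit it. Those predictors are given as examples, and the cited imputation method is not available here. The 18.4% vs 9.8% result is therefore a hypothetical and not the plan. What remains is that the section does not say whether an unsampled abstainer counts as missing at all.

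3. **The effect is small and off the main outcome.** This largely stands. The main outcome is prolonged abstinence, and every figure above is for 7-day abstinence. The validation sentence sits in text covering both outcomes, so a reader might infer that the main result is affected. The documents do not show how cotinine would enter prolonged abstinence, and nothing here sizes such an effect.

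4. **Imputing from sampled abstainers can be optimistic.** People who misreport have reason to avoid the test. If 20% are unsampled and half of those are smoking, the true rates are 0.22 × 0.9 = 19.8% and 0.12 × 0.9 = 10.8%, yet imputation would return about 22% vs 12%. This stands and is a stated cost of the fix.

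**Conclusion.** The concern holds for verified 7-day abstinence (Hypothesis 1.2) and should be fixed. Followed as written, the check can test a different week from the one reported and reads cigarette-abstinent users of other nicotine as smoking. It also leaves self-reported abstainers without a usable sample unscored.

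On the assumed rates, the choice of rule moves the abstinence rates by about 2 to 4 percentage points in SMK-CBI and 1 to 2 in SMK-STD. It costs up to 11 points of power at 20% loss. With equal loss the OR hardly changes; a modest imbalance moves it to 1.92 or 2.18.

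A reader might infer serious bias in the treatment effect. With 25% vs 15% self-reported abstinence, losing 50% of SMK-CBI abstainers and 30% of SMK-STD abstainers gives OR 1.22, and the reverse gives 2.62, against 1.89 with no loss. Those splits are invented, and the documents give no sign of unequal loss. The other-nicotine issue taken alone is minor. The case rests on fixing the rule in advance at low cost, and confidence in its size is limited because every rate and share is assumed.

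**What to change.** (a) At sampling, record the date and re-ask 7-day smoking and current use of NRT or other non-cigarette nicotine.

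(b) Set a maximum interview-to-sample interval, with its length chosen by the study team.

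(c) Before outcomes are seen by arm, fix one score per case:
- In-window result at or above 16 ng/ml, no other nicotine reported and no smoking on re-asking: smoking.
- In-window result at or above 16 ng/ml, non-cigarette nicotine reported and no smoking on re-asking: self-reported cigarette abstinence kept.
- Late sample, or smoking reported on re-asking: handled as uncollected, because it does not check the interview week.
- Uncollected: one stated rule. Either self-report is kept, or verified status is imputed by arm among self-reported abstainers only, with self-reported smokers remaining smokers. Imputation must be confined in this way because self-reported smokers give no saliva and are all scored as smoking, so an ordinary logistic imputation model over everyone would separate on self-report.

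(d) State in E.12.4 which rule applies and whether a late or uncollected sample is a missing abstinence outcome.

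(e) Add two sensitivity analyses: one counting the nicotine-discordant, late and uncollected groups as smoking, and one using self-report alone. Neither should be called a bound on the OR, since unequal loss can move it either way.

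The cost is two short questions and a date at sampling, plus SAP wording. The downside is that late samples are set aside and some main-analysis abstinence rests on self-report, including that of people who both smoke and use NRT. That may be optimistic if people who misreport avoid the test.

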### **Analyses**

**Hypothesis 1.1:** Prolonged abstinence rates will be significantly higher among Veterans in the SMK-CBI group compared to those in the SMK-STD group.

**Hypothesis 1.2:** The 7-day point prevalence abstinence rates will be significantly higher among Veterans in the SMK-CBI group compared to those in the SMK-STD group.

Rates of cigarette abstinence (prolonged abstinence) will be assessed at 6- and 12-month follow-up. Abstinence will be measured as a dichotomous variable that indicates whether patients have been abstinent or not. The same analysis approach will be used to test both prolonged and 7-day point prevalence abstinence rates. Self-report of abstinence will be validated with cotinine saliva testing.

We will use logistic regression to test for a between-group difference in abstinence rates at 6 months. This logistic regression model can be written as:  $\text{Logit}(\pi_i) = \beta_0 + \text{SMK-CBI}_i * \beta_1$ , where  $\pi_i$  represents the probability that patient  $i$  has abstained from smoking at the 6-month follow-up. In this model, SMK-CBI $_i$  is the intervention group indicator; therefore,  $\beta_1$  represents the log-odds ratio of smoking abstinence in the SMK-CBI group as compared to the SMK-STD group. For each of the abstinence outcomes, we will formally evaluate the intervention effect by testing that  $\beta_1$  differs from zero and report the odds ratio ( $\exp(\beta_1)$ ) and 95% CI of the odds ratio. An odds ratio significantly greater than 1.0 provides evidence that SMK-CBI group patients have higher prolonged abstinence rates. The model will also include stratification variables (gender) as recommended in the CPMP guidelines.

Sustainability, or longer term effects of the intervention, will be examined by comparing abstinence rates between groups at 12 months. We will model change in abstinence rates at baseline, 6, and 12 months using generalized linear models with a logit link fit with generalized estimating equations. The regression coefficients from this model have essentially the same interpretation as those from a cross-sectional regression analysis (e.g. logistic regression) but are more appropriate as they properly incorporate the within-subject correlation that is inherent in the longitudinal structure of the data. The model will be fit using the SAS procedure GENMOD (SAS Institute, Cary, NC).

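### Does the 12-month prolonged-abstinence rate fail to measure sustainability because it is not linked to the 6-month result?

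*Combined protocol and SAP*

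**What the plan says.** Section V (Outcomes) names the main outcome: "we will use prolonged abstinence as our main outcome and allow for a grace period around quit date". Two items measure it at both follow-ups, one about daily smoking over a week and the other "In the past 6 months, have you smoked any cigarettes in each of 2 consecutive weeks". Both look back six months. On timing, the same section says "Follow-up surveys will be administered at 6-months and 12 months post-intervention". Counselling comes before that: "Five counseling sessions will be completed over 10-12 weeks on an approximately bi-weekly schedule" (section 6, Research Plan).

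In section VI, under Analyses, abstinence is coded yes or no at each survey. The test for Hypothesis 1.1 is at the first survey: "We will use logistic regression to test for a between-group difference in abstinence rates at 6 months". The later survey is handled separately: "Sustainability, or longer term effects of the intervention, will be examined by comparing abstinence rates between groups at 12 months". A GEE logistic model accompanies it: "We will model change in abstinence rates at baseline, 6, and 12 months". Nothing in the text makes a 12-month success depend on the 6-month result, and the grace period has no stated length or start.

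**The concern.** The two look-back windows sit end to end, so the 12-month answer carries no information about the first six months. Someone who failed at 6 months, stopped by about that survey and stayed abstinent is counted at 12 months together with someone abstinent throughout. A reader who takes sustainability to mean that early quitters stayed quit would be misled, because a 12-month difference could come from maintenance, from later stopping, or from both. The GEE does not settle this: it allows for within-person correlation but estimates the rate at each survey, and two rates do not determine how many people succeeded at both.

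The grace period adds to the unease. The items count back from the survey, not forward from a quit date. Table 1 places the quit-date discussion at different sessions in the two arms: for session 1 of SMK-CBI it lists "All components of SMK-STD Session 1 (to the left, less the quit date discussion", and the date is set at session 2. If an unsupported claim of maintained abstinence were published, the fault would lie in the main outcome.

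**Working it through.** The documents give no abstinence rates, effect size or power calculation for this outcome, so there is no figure of the plan's to reproduce. The check has two parts.

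**1. What each measure covers**

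- The 6-month window runs from about the end of the intervention to month 6, and the 12-month window from about month 6 to month 12. This takes the survey timing in section V at face value.
- Participants who switch from failure to success stopped at about week 1 to week 27 after the intervention. At the 12-month survey they have been abstinent for 52 − 27 = 25 to 52 − 1 = 51 weeks. Someone who stopped clearly after the 6-month survey still fails.
- Smoking during the 10 to 12 weeks of counselling falls before the first window in both arms, so the items as worded already leave it out.

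**2. How far a linked rule could move the result**

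All rates are assumed. The 6-month rates (p6) are 20% SMK-CBI and 12% SMK-STD; the 12-month rates as planned (p12) are 16% and 10%.

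- As-planned 12-month odds ratio: (0.16/0.84) / (0.10/0.90) = 1.71.
- Both-survey rate = p6 × (1 − relapse).
- Switching among 6-month failures = (p12 − both-survey rate) / (1 − p6).

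| Relapse, CBI / STD | Both-survey rate, CBI / STD | Odds ratio | Switching, CBI / STD |
|---|---|---|---|
| 20% / 20% | 16.0% / 9.6% | 1.79 | 0% / 0.45% |
| 50% / 50% | 10.0% / 6.0% | 1.74 | 7.5% / 4.5% |
| 45% / 25% | 11.0% / 9.0% | 1.25 | 6.25% / 1.14% |
| 25% / 45% | 15.0% / 6.6% | 2.50 | 1.25% / 3.86% |

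With equal relapse the two measures nearly agree. The third row needs switching 6.25/1.14 = 5.5 times as common in SMK-CBI; the fourth needs it 3.86/1.25 = 3.1 times as common in SMK-STD.

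Share of 12-month successes who failed at 6 months, at 25% to 45% relapse: 1/16 to 5/16, or 6% to 31%, in SMK-CBI, and 1/10 to 3.4/10, or 10% to 34%, in SMK-STD. The recruitment goals total 371 + 100 = 471. With an assumed 1:1 split (235.5 per arm), these are 2.4 to 11.8 and 2.4 to 8.0 people.

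The rates alone bound the both-survey rate between max(0, p6 + p12 − 1) and min(p6, p12), which is 0 to 16% and 0 to 10%. The zero end requires every 6-month abstainer to relapse.

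A second set of assumptions makes switching equal in the arms at 2% to 10%, with 6-month rates of 18% against 10% or 25% against 15%, and 60% or 80% of abstainers staying abstinent. The linked odds ratio is then 1.78 to 1.93 and the unlinked one 1.33 to 1.76. One case, with 80% staying abstinent and 5% switching:

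- Linked: 0.18 × 0.8 = 14.4% against 0.10 × 0.8 = 8.0%, odds ratio 1.93.
- Unlinked: 14.4% + 0.82 × 5% = 18.5% against 8.0% + 0.90 × 5% = 12.5%, odds ratio 1.59.

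Here linking raises the ratio; in the third row of the table it lowers it. Neither direction nor size follows from the documents.

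**The case for a change.** The best argument for a change is that prolonged abstinence is the main outcome and abstinence at 12 months is part of the first goal. Without a stated rule, the meaning of sustained could be chosen after the data are seen. A both-survey outcome would use items already collected and the existing logistic model. The mediation analysis also takes 12-month abstinence as its outcome without naming the measure, so the ambiguity may carry over.

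The facts in this stand: the items are identical, nothing links them, and the 12-month comparison alone cannot show that individuals maintained abstinence. The step to a fault does not. The plan explains its own term as longer-term effects of the intervention, examined through rates by group, and the first goal in section IV likewise asks about rates at the two times. What is to be sustained is the between-group effect. No goal or hypothesis makes the within-person claim.

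The linked rule also has costs. It fails a person who smoked for a week just after counselling and then abstained for about 51 weeks. It adds another tested 12-month outcome with no stated place among the existing tests, and it relies somewhat more on imputation.

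The grace period is a missing detail. Table 1 gives the session at which a quit date is set (in SMK-STD, only if appropriate), not the date itself, so a shift of about two to three weeks between arms is an inference. The post-intervention windows apply the same rule to both arms in any case.

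**Conclusion.** No change to the plan is needed. The 12-month measure is abstinence over about months 6 to 12 after the intervention, and comparing it between randomised groups answers the longer-term question the plan sets. Linked and rolling six-month abstinence are different estimands on which reasonable statisticians differ, and the documents give no ground for expecting one to show a larger or smaller effect.

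Under the assumed rates, with equal relapse, the choice moves the odds ratio from 1.71 to between 1.74 and 1.79. The wider 1.25 to 2.50 needs strongly unequal relapse and switching between the arms. The test for Hypothesis 1.1 at 6 months and the 7-day outcome are not touched.

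What remains is a matter of description that analysts can handle with data already collected. The Data Summary paragraph plans summaries of all study variables by group and a look at the correlation of the longitudinal outcomes, and a by-arm cross-tabulation of the two surveys fits there, though the plan does not promise one. The report should describe the 12-month rate by the period it covers and should not present it alone as proof that 6-month quitters stayed abstinent.
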